5.8.2 Treatment Compliance

Compliance to CAM2029 or placebo will be summarized using the following parameters based on the data collected in the EDC system in the double-blind treatment period:

- Percent compliance, calculated as:
$$(\text{Total number of injections taken}) / (\text{Total number of planned injections}) \times 100$$

where the total number of planned injections is calculated as the number of weeks that the patient has been treated from Day 1 or the number of weeks from Day 1 to the last completed planned visit, whichever is the last.
- Percent compliance categories, $<80\%$, ≥ 80 and $<120\%$, $\geq 120\%$

The above parameters will be summarized for each treatment group, the combined active treatment groups, and overall (i.e., all treatment groups pooled together). A listing of the exposure and compliance parameters will also be provided. Patient diary data will also be present in listings.

5.9 Efficacy Endpoints and Analyses

All efficacy data will be included in data listings and summary tables and/or figures. The efficacy analyses of the double-blind treatment period will be performed using the ITT, FAS, and PPS, as described in the following sections. The combined active treatment groups will be summarized for efficacy analyses during the double-blind treatment period. Patients will be analyzed according to the treatment assigned at randomization except for summaries based on the PPS, where patients will be analyzed according to the actual treatment given.

Kidney-related variables, i.e., total kidney volume and eGFR, will also be analyzed for patients with presence of kidney cysts and summarized by treatment arm, combined active treatment groups, and overall.

5.9.1 Multiple Testing Procedure

See [Section 3.1](#).

5.9.2 Primary Efficacy Objective, Endpoint, and Estimand Analysis

The primary objective is to evaluate the treatment effect of CAM2029 compared to placebo on liver volume in patients with PLD.

The estimand for the primary objective is defined by the attributes described in [Table 1](#).

The analysis will be primarily performed on the ITT analysis set.

5.9.2.1 Definition of the Primary Endpoint

The primary efficacy endpoint is defined as the change from baseline to Week 53 in htTLV as determined by MRI volumetry. Depending on the shape of the distribution of htTLV, data may be logarithm-transformed prior to analysis. After analysis of log-transformed data, the estimated parameters will be transformed back to the original scale using the exponential function, thus producing estimated geometric means and estimated ratio of means which will be presented together with 95% CIs.

5.9.2.2 Main Analytical Approach

The combined estimand is defined in [Table 1](#) and incorporates two main types of events that influence how the treatment effects are estimated, i.e. initiation of another SRL or therapeutic intervention with the intention to reduce the liver size and permanent discontinuation of IMP.

Missing values will be imputed using the MI method described in the [Section 5.3.1](#). Missing Week 53 data will be imputed using MI assuming that data are missing at random within the groups used for imputation.

For each of the imputed datasets, the primary efficacy endpoint will be analyzed using an ANCOVA model with fixed factor for treatment and baseline htTLV as covariate, within the

framework of a MI method. The main comparison will be between the average effect of the 2 CAM2029 doses compared to placebo (i.e., the contrast for the treatment difference is $(0.5 \ 0.5 \ 0) - (0 \ 0 \ 1)$ where the 2 CAM2029 doses are given by the first two terms and placebo by the last). Additionally, each of the doses of CAM2029 will be compared with placebo separately as described in [Section 3.1](#). For SAS code, see [Appendix 1](#).

[figure not shown]
The estimated difference in mean change from baseline (average effect of combined CAM2029 – placebo) will be derived together with the associated standard error. The estimates and the standard errors from the 100 analyses will be combined to one estimate and associated standard error in PROC MIANALYZE using Rubin's rule. The resulting p-value will be reported. The combined estimated mean difference in change from baseline and associated 95% CI will also be reported.

Descriptive summary statistics of observed values and mean change from baseline to Week 53 in htTLV will also be presented by treatment groups.

5.9.2.3 Sensitivity Analyses

Tipping Point

If a significant difference can be detected from the primary analysis, a tipping point analysis (4) will be performed to investigate the robustness of departures from the MAR assumption in the MI model by applying a specified sequence of shift parameters that modify the imputed htTLV values.

Last Observation Carried Forward (LOCF)

The primary endpoint will be analyzed using the same ANCOVA model as described above for the primary analysis, but missing data will be imputed using last observed values post-baseline.

Mixed Model Repeated Measures (MMRM)

Analysis of Covariance (ANCOVA), Observed Cases (OC)

Similar to the primary efficacy analysis above, the primary endpoint will be analyzed using the same ANCOVA model with fixed factor for treatment and baseline htTLV as a covariate based on OC without imputation or handling of intercurrent events. The analysis will be performed on the ITT analysis set.

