8.9.2.1 Sensitivity Analyses

The following sensitivity analyses will be performed on the primary endpoint:

[figure not shown]
- Last observation carried forward analyzed in an ANCOVA with fixed factors for treatment and the baseline value as covariate, i.e., missing data will be imputed using last observed values post-baseline.
- A mixed model repeated measures model will be used to estimate the change from baseline.

- The primary endpoint will be analyzed using the same ANCOVA model with fixed factor for treatment and baseline htTLV as a covariate based on observed cases without imputation or handling of intercurrent events.
- If a significant difference can be detected from the primary analysis, a tipping point multiple imputation analysis as described in Ratitch et al. (2013) will be applied (52). A tipping point analysis is a means of exploring the influence of missingness on the overall conclusion by investigating a broad range regarding the missingness mechanism (from less conservative to more conservative, i.e., it will include scenarios where dropouts on CAM2029 have worse outcomes than dropouts on placebo). The analysis finds a (tipping) point in this range, at which conclusions of effect vary from being favorable to the treatment with CAM2029 to being unfavorable. Based on such a tipping point, clinical judgment can be applied as to the plausibility of the assumptions underlying this tipping point.

Sensitivity analyses will be described in detail in the SAP.

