8.9.2.2 Supplementary Analyses

The following supplementary analyses will be performed on the primary endpoint:

Supplementary analyses will be described in detail in the SAP.

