2.1 Objectives, Endpoints, and Estimands

Table 1: Primary objective, endpoint and estimand

Primary Objective	Primary Endpoint / Estimand

To evaluate the treatment effect of CAM2029 compared to placebo on liver volume in patients with PLD	
Endpoint: Change from baseline to Week 53 in htTLV as determined by MRI volumetry
 
Estimand: The primary estimand of interest is the mean change from baseline to Week 53 in htTLV comparing 2 doses of CAM2029 to placebo in patients with PLD, had no patients started treatment with alternative SRL or undergone any therapeutic intervention with the intention to reduce the liver size, and is defined by the following attributes:
 
Treatment condition: The primary treatment condition of interest is the average effect of:
The CAM2029 treatment (10 mg once weekly and 10 mg every 2 weeks) vs placebo treatment 
Thereafter, the treatment conditions of interest are the effects of:
 
CAM2029 10 mg once weekly vs placeboCAM2029 10 mg every 2 weeks vs placebo 
Target population: The population targeted by the clinical question is defined as patients in the ITT analysis set as defined by the inclusion/exclusion criteria in the trial protocol.Variable (endpoint): The variable addressing the primary clinical question is change from baseline in htTLV as assessed at Week 53.Handling of intercurrent events: Intercurrent events will be handled through a combination of a treatment policy strategy and a hypothetical strategy depending on other treatment received and therapeutic interventions conducted while still in the trial:

Primary Objective	Primary Endpoint / Estimand

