	
• IMP treatment discontinuation: Patients who discontinue treatment with IMP and do not receive another SRL or have any therapeutic interventions with the intention to reduce the liver size while still in the trial will be analyzed by the treatment policy strategy, i.e., observations collected after IMP discontinuation will be included in the analysis as they were collected. For patients who discontinue treatment with IMP and start receiving another SRL or have any therapeutic intervention with the intention to reduce the liver size while still in the trial, only observations collected prior to the start of the SRL and the therapeutic intervention will be included in the analyses. Observations collected after the start of the SRL and the therapeutic intervention will be handled using the method described below.• Use of another SRL (see Appendix 12): Patients who receive an SRL other than the trial IMP while still in the trial, will be handled according to a hypothetical strategy. That is, any measurements of htTLV following the start of any other SRL administration will be set to missing and not used in the analysis. This hypothetical strategy is motivated by the fact that no approved alternative SRL treatment for PLD is available in most countries.• Therapeutic interventions: Patients undergoing therapeutic intervention with the intention to reduce the liver size while still in the trial will be handled according to a hypothetical strategy. That is, measurements of htTLV following this intercurrent event will be set to missing and not used in the analysis. This strategy is motivated by the fact that such interventions may directly impact the primary endpoint without being related to the effect of the IMP.• Missing values: If the htTLV cannot be determined at Week 53, either due to start of another SRL treatment or after a therapeutic intervention with the intention to reduce the liver size after IMP discontinuation or values are missing for other reasons, missing values will be imputed using the MI method described in the Section 5.3.1 and Section 5.9.2.2. 
5. Population-level summary for comparison between treatment conditions: Mean change from baseline to Week 53 in htTLV

Table 2: Key Secondary objective, endpoint and estimand

[figure not shown]
[figure not shown]
Key Secondary Objective	Key Secondary Endpoint / Estimand

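### The observed-case ANCOVA is labelled a sensitivity analysis, but it switches the intercurrent-event strategy as well as the missing-data handling, so a difference from the primary result cannot be put down to missing data alone

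*SAP*

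**What the plan says.** The primary estimand (SAP 2.1, Table 1; Protocol 8.9.2) asks what the mean change in htTLV would be "had no patients started treatment with alternative SRL or undergone any therapeutic intervention with the intention to reduce the liver size". For another SRL, the rule is that "any measurements of htTLV following the start of any other SRL administration will be set to missing and not used in the analysis". For a therapeutic intervention aimed at liver size, "measurements of htTLV following this intercurrent event will be set to missing and not used in the analysis", because "such interventions may directly impact the primary endpoint without being related to the effect of the IMP". The values set to missing are then multiply imputed. IMP discontinuation without either event follows treatment policy, so its later values stay in.

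Protocol 8.9.2.1 opens its list with "The following sensitivity analyses will be performed on the primary endpoint". One entry is the same ANCOVA model "based on observed cases without imputation or handling of intercurrent events". SAP 5.9.2.3 repeats this ("based on OC without imputation or handling of intercurrent events") and specifies the ITT set.

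The protocol has a separate class of analysis in 8.9.2.2 ("The following supplementary analyses will be performed on the primary endpoint"), and SAP 5.9.2.4 carries the same heading. The content of both is not visible in the public text.

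**The concern.** A sensitivity analysis should hold the clinical question fixed and vary an assumption behind the answer. Here the obvious assumption to vary is that values are missing at random within arm. The observed-case run does drop the imputation, but it also brings back liver volumes that the plan excludes because they may not reflect the IMP. It answers a different question from the primary estimand.

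If the two results differ, the reader cannot separate the effect of imputation from the effect of the restored values. If they agree, two opposing shifts may have cancelled. The direction is not fixed either. A liver-reducing event in a placebo patient shrinks the apparent benefit, and one in a CAM2029 patient enlarges it.

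Such values can exist. Patients who stop IMP are followed with all assessments to Week 53 (Protocol 4.1.2 and 6.10.1), and SRLs are used off-label for symptomatic PLD (Protocol 2.1.1).

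**Working it through.** **Step 1: compare the rules.**

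| Situation at Week 53 | Primary analysis | Observed-case ANCOVA |
|---|---|---|
| IMP stopped, no other SRL or intervention, value observed | kept | kept |
| Value observed after another SRL | set to missing, imputed | kept |
| Value observed after a liver-reducing intervention | set to missing, imputed | kept |
| Value not observed | imputed | patient dropped |

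Rows 2 and 3 change the intercurrent-event strategy. Row 4 changes the missing-data handling. Row 1 does not differ, so the divergence is confined to other SRLs and interventions.

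**Step 2: reproduce the planning figures** (Protocol 8.2, SAP 6; residual SD 180 mL/m, two-sided 5% t-test, noncentral t).
- 20 vs 20 at 165 mL/m: power 0.806 (stated 80%).
- 40 vs 20 at 165 mL/m: 0.908 (stated about 90%).
- 40 vs 20 at 141 mL/m: 0.803 (stated about 80%).
- Smallest significant difference at 20 vs 20: 115.2 mL/m (stated about 115).

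The point does not depend on these figures, but they support using 165 and 180 as inputs.

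**Step 3: plausible shifts, S.**
- *Another SRL.* Protocol 2.1.1 cites a meta-analysis with TLV 0.15 L lower on treatment. At an assumed height of 1.6 to 1.8 m this is 150/1.8 = 83 to 150/1.6 = 94 mL/m, say 90. Protocol 8.2 gives about 235 mL/m for pasireotide against placebo over 12 months. Range used: 90 to 235 mL/m.
- *A procedure.* The documents give no figure. Assumed 500 mL/m, range 200 to 800.

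**Step 4: effect on the estimate.** Inputs are 69/3 = 23 per arm, true difference -165 mL/m, no other missing data, and m = 2 affected placebo patients (assumed, since no event rate is given). Keeping their values lowers the placebo mean by S × m/23, so the expected observed-case estimate is -165 + 2S/23. The share of significant trials comes from simulating the three-arm ANCOVA with the planned contrast.

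| Event kept in | S (mL/m) | Estimate (mL/m) | Significant |
|---|---|---|---|
| Another SRL | 90 | -165 + 7.8 = -157.2 | about 92% |
| Another SRL | 235 | -165 + 20.4 = -144.6 | about 85% to 87% |
| Procedure | 200 | -165 + 17.4 = -147.6 | about 87% |
| Procedure | 500 | -165 + 43.5 = -121.5 | about 66% |
| Procedure | 800 | -165 + 69.6 = -95.4 | about 34% |
| Same values set to missing | n/a | -165 | about 93% |

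Simulated means agree with the formula to within about 2 mL/m; the 85% to 87% is the spread between runs. The last row can be checked directly for 46 vs 21: 165/(180 × √(1/46 + 1/21)) = 165/47.4 = 3.48, which gives power of about 93%. That row assumes the events are unrelated to outcome.

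**Step 5: the other direction.** With 2 of the 46 CAM2029 patients affected at S = 500, the estimate is -165 - 500 × 2/46 = -186.7 mL/m, an overstatement.

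**The case against.** The case on the other side is substantial.

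- **The rule is disclosed.** Both documents say openly that intercurrent events are not handled. This stands: nobody is misled about the data used, only about what a comparison with the primary result can show.
- **Missing at random is tested elsewhere.** SAP 5.9.2.3 makes the tipping-point analysis the check on that assumption, and LOCF and MMRM are also listed. This stands, with the limit that the tipping-point analysis runs only if the primary result is significant. A reader might infer that the assumption goes untested; the documents do not support that.
- **The events may be few.** Inclusion criterion 5 (Protocol 5.2) admits only patients who are not candidates for, or not willing to undergo, surgery for hepatic cysts during the trial. This should make procedures uncommon.
- **Affected patients can be traced.** Interventions that count are to be defined before database lock (SAP 5.1), and medications and procedures are listed by patient (SAP 5.7). This helps, but tracing after the fact does not replace a pre-specified analysis.
- **Simple deletion may itself be biased.** If patients with the fastest-growing livers are the ones who have procedures, dropping their values is not neutral, and the illustration cannot show this. It stands as a limit on the last row of the table. It also means that the corrected observed-case run is only a mild test of the primary assumption.
- **The supplementary analyses and the SAP's MMRM detail are not visible.** The cleaner run may already exist there. No claim is made about that text.

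**Conclusion.** The point holds as a matter of labelling and interpretation. The observed-case ANCOVA changes the estimand and the missing-data handling together, by a stated rule in both documents, and so does not isolate sensitivity to missing data.

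Its size depends on events that the documents do not quantify. With none, it is zero. With 2 affected placebo patients, another SRL moves the estimate by about 8 to 20 mL/m out of 165, with little loss of significance. Only a procedure with a large assumed shift moves it by 40 mL/m or more.

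Three stronger readings are not supported:
- **That the primary result is compromised.** The primary analysis applies its own rules, and this analysis has no place in the testing sequence (SAP 3.1).
- **That one or two patients switching SRL could overturn the robustness picture.** At the effect sizes that the protocol itself cites, they would not move it far.
- **That the key secondary endpoint PLD-S has the same defect.** It is analysed with the same methods, but its estimand is not visible, so its intercurrent-event rules are unknown.

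**What to change.** In SAP 5.9.2.3, state that htTLV values after another SRL or a therapeutic intervention are set to missing under the Table 1 rules before the observed-case ANCOVA is run without imputation. That run then differs from the primary analysis only in its missing-data handling.

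Keep the as-collected analysis, but list it under Supplementary Analyses (SAP 5.9.2.4). Describe it as including values after another SRL or intervention, that is, treatment-policy handling among patients with observed Week 53 data. It should not be called a full treatment-policy analysis, because patients without a Week 53 value are left out.

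Align Protocol 8.9.2.1, or record the departure in SAP 5.15; Protocol 8.1 allows the SAP to amend the proposed analyses. Make the same change for PLD-S only if its estimand uses the same intercurrent-event rules.

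The cost is one sentence, one extra ANCOVA run and one more table, with no new data. SAP 2 allows changes until database lock and unblinding for the primary analysis.

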5.9.2.4 Supplementary Analyses

5.9.3 Key Secondary Efficacy Endpoint and Estimand

The estimand definitions applicable to secondary objectives are described in [Table 2](#).

[figure not shown]
The PLD-S is a PRO currently under development to assess patient reported symptoms of PLD. [REDACTED]

[figure not shown]
The key secondary efficacy endpoint is change from baseline to Week 53 in the PLD-S measure score and this endpoint will be analyzed with the same methods as for the primary endpoint. In the analysis of the key secondary efficacy endpoint, the main comparison will be between the average effect of the 2 CAM2029 doses compared to placebo. In addition, the 2 doses of CAM2029 will be compared with placebo separately as described in [Section 3.1](#).

5.9.4 Secondary Efficacy Endpoints and Estimands Analysis

The estimand and endpoint definitions applicable to secondary objectives are described in [Table 3](#).

[figure not shown]
[REDACTED]

[figure not shown]

[figure not shown]

5.9.5 Exploratory Efficacy Endpoint(s) and Estimands Analysis

The following exploratory efficacy endpoints will be analyzed:

[figure not shown]

5.9.6 Subgroup Efficacy Analyses

Primary endpoint and key secondary endpoint data from subgroups of patients in the ITT will be analyzed as specified below. These analyses will comprise descriptive summaries; the goal will be to identify signals of additional effects that the primary analysis does not consider. Such analyses will be considered exploratory and will not involve hypothesis testing.

Prespecified subgroup analyses will be conducted for:

- Age 
- Sex (Male, Female)

5.10 Safety Endpoints and Analyses

Safety analyses will be performed for the treatment period based on the safety analysis set (SAF).

AEs starting in the double-blind period and ongoing at the first dose in the extension period will be assigned to the double-blind period and not to the extension period. This is to avoid counting the same AE twice.

5.10.1 Adverse Events

AEs will be coded using MedDRA version 25.0 (or higher version if updated during the trial or in relation to DBL and agreed with the Sponsor), associating lowest level terms (LLTs) with PTs and SOC by the primary hierarchy. TEAEs are defined as AEs that started or worsened after the first administration of IMP and to the EOT visit or start of another SRL treatment, whichever comes first. Furthermore, the onset date of an TEAE should be prior to the date of last dose of IMP + 5 half-lives (5x10.6 days).

TEAEs, presented as SOC and PTs, will be further defined:

- Treatment period TEAEs are defined as:
 - For patients enrolled into the extension period: TEAEs that occur or worsen on or after the date of first IMP administration in the treatment period and before the date of the first IMP administration in extension period.
 - For patients early terminated from the IMP in the treatment period: all TEAEs reported are double-blind treatment period TEAEs.

The severity of all AEs will be graded using the latest version of the National Cancer Institute Common Terminology Criteria for Adverse Events (CTCAE). Missing severity will be summarized as a separate category.

IMP-related TEAEs are assessed as “Probably related” and “Possibly related”. If the causal relationship to the IMP is missing, the event will conservatively be assigned as related to IMP.

TEAEs of special interest (TEAESI) will be defined pre-DBL as applicable.

An overall AE summary will be presented using the number and percent of patients, and number of events with the following:

- Any AE
- Any TEAE
- Any IMP-related TEAE, including events assessed as “Probably related” and “Possibly related”, or missing relationship to the IMP on the eCRF
- Any TEAE by CTCAE Grade
- Any IMP-related TEAE of CTCAE Grade ≥ 3
- Any TESAE
- Any IMP-related serious TEAE
- Any TEAEs leading to withdrawal from the trial
- Any TEAE leading to IMP discontinuation, including events with action taken with trial treatment = “Drug withdrawn” on the eCRF and TEAEs leading to withdrawal from the trial

- Any TEAE leading to death, including events with outcome = fatal on the eCRF
- Any TEAESI
- TEAESIs of CTCAE Grade ≥ 3
- Any injection site TEAE
- Any related non-injection site TEAESIs
- Any TEAE related to COVID-19

TEAEs will be summarized by trial period, SOC, and PT, with the number and percentage of patients and the number of events, where applicable.

The tables will display the number and percentages of patients who reported at least one AE in each SOC. Within each SOC, the tables will display the number and percentages of patients reporting at least one AE as designated by the PT. The outputs will be presented by descending frequency across all patients for a given SOC and PT. At each level of summarization, a patient will be counted once if he/she reported one or more events. The severity grade to the IMP will be summarized in a similar manner. For example, if a patient reports multiple AEs, the patient will be represented in the most severe category.

All AEs will be listed. TEAEs and non-TEAEs will be listed separately.

